2.3.4.5 PGIC and PGIS scales

The Patients' Global Impression of Change (PGIC) scale and the Patients' Global Impression of Severity (PGIS) scale represent clinically relevant tools to assess perceived impact of disease management. The PGIC evaluates overall health status as perceived by the patient in a seven-point, single-item scale including 'very much better', 'moderately better', 'a little better', 'no change', 'a little worse', 'moderately worse', and 'very much worse'. The PGIS includes 4 severity scales (none, mild, moderate, and severe) and patients are asked to rate their overall severity of symptoms in the present (e.g., at each visit). The PGIC and PGIS are the most commonly used anchor based method of assessing clinically important change and severity in which the external judgment of meaningful change is made by the patient (see Appendix E of the protocol). The PGIC and PGIS evaluations will be done on subjects' device at the clinic PRIOR to dosing.

2.3.4.6 EQ-5D-5L

The EuroQol-5D-5L (EQ-5D-5L) is a standardized measure of health status developed by the EuroQol Group in order to provide a simple, generic measure of health for clinical and economic appraisal (see Appendix F of the protocol). The EQ-5D-5L is to be done on a subject's device at the clinic PRIOR to dosing. EQ-5D-5L consists of two parts:

- EQ-5D-5L descriptive system

- Visual Analog Scale (VAS) with instant recall of "how you feel today"; scale goes from 0-100, where 100 means the best health you can imagine and 0, the worst one.

The EQ-5D-5L descriptive system includes the basic domains common to each generic health status measure: mobility, self-care, usual activities, pain/discomfort and anxiety/depression. The instrument includes one single question per domain. For each question, there are 5 levels of responses, corresponding to increasing levels of impairment (no problems, slight problems, moderate problems, severe problems, and extreme problems), and coded 1 to 5

2.3.5 Safety Endpoints

- Proportion of patients with AEs, serious AEs (SAEs), severe hematologic AEs, severe non-hematologic AEs, and AEs leading to discontinuation.
- Proportion of subjects with thrombolysis in myocardial infarction (TIMI) major bleeding event.
- Description and frequency of events of special interest by
 - Serious infections.
 - Severe injection-related reactions.
 - Gastrointestinal perforations.
 - Hypersensitivity reaction during study drug administration.
 - Anaphylaxis occurring at any time, even if considered unrelated to the study drug.
 - Neutrophil < 500/mm³ (severe) or neutrophil < 1000/mm³ (severe) with evidence of concurrent infection. These events will be separately summarized by treatment group and dose.
 - Thrombocytopenia (platelet count < 50,000/mm³ [severe]) or platelet count < 75,000/mm³ (moderate) with evidence of concurrent TIMI major bleeding. These events will be separately summarized by treatment group and dose.
 - Malignancies
- Description of additional safety assessments by treatment group and dose: vital signs, ECG, clinical laboratory, and anti-drug antibodies (binding and neutralizing).

3 STATISTICAL METHODOLOGY

3.1 General Considerations

3.1.1 Analysis Day

Analysis day will be calculated from the date of first dose of study drug. The day of the first dose of study drug will be Day 1, and the day immediately before Day 1 will be Day -1. There will be no Day 0.

3.1.2 Analysis Visits

Scheduled visits will be assigned to analysis visits as recorded in the electronic data capture (EDC) system. If a scheduled visit is not available, unscheduled and early termination visits will be assigned to analysis visits using analysis visit windows based on the actual date the assessment took place. The low analysis day of the analysis window will be calculated as the midpoint between the scheduled assessment and previously scheduled assessment for that parameter. The high analysis day of the analysis window will be calculated as the midpoint between the scheduled assessment and the next scheduled assessment for that parameter.

Where multiple measurements for a particular parameter appear within an analysis window, the scheduled visit will be used. If no scheduled visit appears in the analysis window, the result closest to the target day will be used. If equidistant and both are unscheduled and/or early termination visits, the later result will be used for the summary measure. For applicable efficacy parameters, "End of Treatment" visit will be derived where the average of assessments at Week 23 and Week 24/ET visits from the EDC will be calculated. Otherwise Week 24/ET visit will be used as the derived "End of Treatment" visit.

Analysis Visit	Target Day	Low Analysis Day	High Analysis Day
Baseline	1		1
Week 2	8	2	14
Week 4	22	15	28
Week 5	35	29	42
Week 7	49	43	55
Week 9	63	56	70
Week 13	85	71	99
Week 17	114	100	128
Week 21	141	129	153
Week 23	157	154	161
Week 24	165	162	168
End of Treatment	161	154	168
Week 28	190	169	211
Week 32	224	211	236

The observational period for the study will start from informed consent and end with study completion. Any event occurring after the defined observational period, even if collected on the case report form (CRF), may not be included in the planned statistical analyses. However, all data, including that reported after the defined observational period, will be included in the patient data listings.

3.1.3 *Definition of Baseline*

For the primary endpoint hs-CRP, baseline will be the average of the hs-CRP value prior to randomization and Day 1. For SAA, baseline will be calculated as the average of the values at Visit Week -1 and Day 1. For laboratory parameters hemoglobin and serum albumin, baseline will be calculated as the average of two most recent lab values prior to randomization and Day 1. For NT-pro-BNP, baseline will be calculated as the average NT-pro-BNP value prior to randomization and Day 1. For the CARES Corvidia ePRO items, baseline will be the average of 7 consecutive measurements (Day -7 to Day -1) prior to first dose initiation. For all other evaluations that are collected at multiple occasions prior to initiation of Study Drug, the latest evaluation will be considered the baseline evaluation for analysis, unless otherwise specified. Similarly, end of treatment values will be calculated by taking the average of assessments taken at Week 23 and Week 24.

3.1.4 *Summary Statistics*

All study-collected data will be summarized by treatment group for the appropriate analysis population, using descriptive statistics, graphs, and/or raw data listings. Descriptive statistics for continuous variables will include number of patients (n), mean, standard deviation (SD), median, quartiles (Q1 and Q3), minimum (min) and maximum (max) values. Analysis of categorical variables will include frequency and percentage.

3.1.5 *Handling of Dropouts and Missing Data*

Missing data will be imputed only in the context of sensitivity analysis as described in section 3.4.1.

3.2 Analysis Populations

3.2.1 *Intent-to-Treat (ITT) Analysis Population*

The ITT analysis population includes all randomized patients and will be the primary population for analyses of disposition, baseline, and efficacy data.

3.2.2 *Per-Protocol (PP) Analysis Population*

The PP analysis population will be the secondary population for analyses of disposition, baseline data, and efficacy data. For PP analysis population, treatment classification will be based on the randomized treatment. PP analysis population is defined as all randomized patients who completed the study and did not incur a significant protocol violation. Significant protocol violations may include but are not limited to:

- Failed to meet eligibility criteria
- Took the wrong study drug (i.e., did not take the randomized study drug)
- Had study drug compliance <80%
- Took a restricted concomitant medication
- Failed to complete the primary efficacy assessment

A list of subjects with significant protocol violations leading to exclusion from PP analysis population will be finalized prior to unblinding the randomized treatment assignments.

3.2.3 *Safety Analysis Population*

The Safety analysis population is defined as all randomized patients who received at least one dose of study drug. All safety data will be analyzed using the Safety analysis population. For the Safety analysis population, treatment classification will be based on the actual treatment received.

3.2.4 *Pharmacokinetics (PK) Analysis Population*

The PK analysis population is defined as all randomized patients who received at least one dose of study drug and had at least one post-dose PK blood sample. For the PK analysis population, treatment classification will be based on the actual treatment received.

3.3 Subject Data and Study Conduct

3.3.1 *Subject Disposition*

Counts and percentages of subjects who were randomized, discontinued early from the study, and completed the study will be summarized by treatment and in total based on all randomized subjects (ITT analysis population). Reasons for early discontinuation will also be summarized.

3.3.2 *Protocol Violations*

Protocol deviations are defined in the Protocol Deviation Plan and classified as CSR reportable or non-CSR reportable. All protocol deviations will be listed.

3.3.3 *Demographic and Baseline Characteristics*

The following demographic and baseline characteristics will be summarized:

- Age (years)
- Sex
- Race
- Ethnicity
- Height (cm)
- Weight (kg)
- Body mass index (BMI) (kg/m²)
- Baseline Hemoglobin (>=11 or <11 g/dL)
- CKD Stage (Stage 3, Stage 4 or Stage 5)

Demographic and baseline characteristics will be summarized with descriptive statistics or counts and percentages of subjects as appropriate by treatment and in total for the ITT, per-protocol, and safety analysis populations.

3.3.4 *Medical History*

Medical history will be coded to system organ class and preferred term using the Medical Dictionary for Regulatory Activities (MedDRA) Version 21.0. Counts and percentages of subjects with medical history by system organ class and preferred term will be summarized by treatment and in total based on the ITT analysis populations.

3.3.5 *Prior and Concomitant Medications*

Prior and concomitant medications will be coded to anatomical therapeutic chemical (ATC) class and preferred term using the World Health Organization (WHO) Drug Dictionary. For summary purposes, medications will be considered prior medications if they were given before the first dose of study drug and concomitant medications if they were taken before and were continuing after the first dose of study drug or initiated after the first dose of study drug.

If a medication has incomplete start or stop dates, dates will be imputed to determine whether a medication should be considered prior or concomitant. If a medication start date is incomplete, the first day of the month will be imputed for missing day and January will be imputed for missing month. If a medication stop date is incomplete, the last day of the month will be imputed for missing day and December will be imputed for missing month. Incomplete start and stop dates will be listed as collected without imputation.

Counts and percentages of subjects taking prior and concomitant medications by Anatomical therapeutic class (ATC) and preferred term will be summarized by treatment and in total based on the Safety analysis population. Patients will be counted only once by medication class or name.

3.3.6 Study Drug Exposure

Weeks of exposure to study drug will be calculated as: (date of last dose of study drug – date of first dose of study drug + 1)/7. Note that the exposure calculation is intended to describe the length of time a subject was exposed to study drug and therefore does not take study drug interruptions into account. Weeks of exposure to study drug will be summarized by treatment based on the Safety analysis population with descriptive statistics.

Study drug is planned to be administered every 28 days for a total of 6 treatments on Weeks 1, 5, 9, 13, 17, and 21.

Counts and percentages of number of injections received (1 to 6) along with summary statistics will be summarized by treatment based on the Safety analysis population.

3.4 Efficacy Assessment

For all efficacy variables, the number of patients (n), mean, standard deviation (SD), median, quartiles (Q1 and Q3), minimum (min) and maximum (max) values for the observed value, change from baseline, and percent change from baseline (as applicable) will be reported. The difference (Ziltivekimab - Placebo) in changes or percent changes (as applicable) will be presented.

A mixed model for repeated measures (MMRM) will be used to evaluate change (or percent change) from baseline. The model will include variables for baseline hemoglobin (≥ 11 or < 11 g/dL), CKD Stage (3, 4 or 5), treatment group, visit and treatment group-by-visit interaction as categorical fixed effects, baseline value and baseline-by-visit interaction will be included as covariates. The least squares means for each dose, the least squares mean differences from placebo along with the associated 95% confidence intervals (CIs) and p-values will be presented. If the normality assumption is not met, a nonparametric test will be selected for efficacy analysis.

An unstructured covariance matrix will be used to model the within-subject correlation. The Kenward-Roger approximation will be used to adjust the denominator degrees of freedom. The analysis will be performed based on all observed post-baseline scores without any imputation of missing data. In the case when the MMRM fails to converge using an unstructured covariance matrix in any stage, a less stringent covariance matrix (e.g., autoregressive 1) will be used.

Sensitivity analyses will be conducted to explore the robustness of the result for primary efficacy endpoint based on MMRM. Efficacy data will be summarized by randomized treatment group based on the ITT and PP analysis populations.

The differences in proportions and 95% CIs will be based on the normal approximation to binomials.

Missing data will be imputed only in the context of sensitivity analysis as described in section 3.4.1.

The pharmacodynamic efficacy of three Ziltivekimab doses compared to placebo will be assessed by evaluating the following:

3.4.1 Primary Efficacy Endpoint

Primary Analysis

The primary analysis variable is the difference in percent change in hs-CRP levels from baseline (average of the hs-CRP value prior to randomization and Day 1) to the Week 13 between each active group and placebo.

The primary efficacy analysis will be carried out using a mixed model for repeated measures (MMRM) to evaluate percent change in hs-CRP levels from baseline in the ITT populations. The MMRM model will include percent change in hs-CRP from baseline as the dependent or response variable, variables for baseline hemoglobin (≥ 11 or < 11 g/dL), CKD Stage (3, 4 or 5), treatment group, visit and treatment group-by-visit interaction as categorical fixed effects, baseline value and baseline-by-visit interaction will be included as covariates. Restricted Maximum Likelihood (REML) method will be used.

The sample SAS code can be found below:

```
*****
*Note: PCHG = Percent change in hs-CRP from baseline
*      HGB = Baseline Hemoglobin category (>=11 or <11g/dL)
*      CKD = CKD Stage (3, or 4/5)
*      TRT = Treatment group
*      VISIT = Analysis visit
*      TRT*VISIT = Treatment group by visit interaction
*      BASE = Baseline value
*      BASE*VISIT = Baseline by visit interaction
*      USUBJID = Unique subject identifier
*****;
proc mixed data=efficacy method=reml covtest;
  class HGB CKD TRT VISIT;
  model PCHG = HGB CKD TRT VISIT TRT*VISIT BASE BASE*VISIT/
    DDFM=KENWARDROGER;
  repeated / type=un subject=USUBJID;
  ODS OUTPUT LSMeans=lsmeantable Diffs=LSDiffs;
run;
```

The treatment difference in terms of mean percent change from baseline will be estimated and tested in this MMRM model. The least squares means for each dose, the least squares mean differences from placebo along with the 95% confidence intervals (CIs) and p-values will be presented from the above results.

Normality assessment for the primary efficacy variable will be performed using the Shapiro-Wilk test. Normality test will be performed on the model residuals. If substantial deviation from assumption of normality is encountered (Shapiro-Wilk p-value < 0.01), a nonparametric analysis will be performed. Median and quartiles will be presented for hs-CRP values at baseline, Week 13, and percent change in hs-CRP from baseline to Week 13. The Hodges-Lehmann estimator of the location shift between each treatment arm and placebo will be presented. The asymptotic 95% confidence limits for the location shift and p-value from the Wilcoxon test will also be presented. The nonparametric analysis will account for the covariates baseline hemoglobin (≥ 11 or < 11 g/dL) and CKD Stage (3, 4 or 5) by aligning responses within each stratum defined by the covariates prior to analysis.

The SAS code for Hodges-Lehmann estimates is listed below:

```
proc npar1way hl alpha=.05 align=strata(hl);  
  class TRT;  
  strata HGB CKD;  
  var PCHG;  
  ods output wilcoxontest=WILT hodgeslehmann=HL1;  
  run;
```

Sensitivity Analyses

Sensitivity analyses will be performed on the PP analysis population with the same method used to analyze the primary efficacy endpoint. In addition, a sensitivity analysis will be performed on the ITT analysis population using a pattern-mixture model using sequential modeling with multiple imputation to assess the robustness of the primary MMRM results to the possible violation of the missing-at-random (MAR) assumption. The sensitivity analysis will consider dropout reasons while imputing missing values after the discontinuation. Subjects who discontinued due to lack of efficacy or adverse events in the active arms are assumed to have no treatment effect after the discontinuation. These subjects are assumed to copy the profile of placebo arm and missing values are imputed based on the distribution estimated from the placebo group under the missing not at random (MNAR) using copy-reference approach. The rest of missing values in the placebo arm and active arms will be imputed using the observed data in their respective group under the MAR assumption. The multiple imputation model will include factors such as treatment arm, baseline hemoglobin category and CKD stage in addition to the data outcomes at each visit.

The following steps will be performed:

Step 1 Intermittent (non-monotone) missing data will be imputed using the MCMC option of SAS PROC MI (using seed=5414).

Step 2 For monotone missing data, the values for each pattern will be imputed via the chained equation method with range restriction, using SAS PROC MI option MONOTONE REG ().

Under step 2, missing values for subjects who discontinued due to lack of efficacy or adverse events will be imputed under MNAR assumption using copy-reference approach, and missing values for subjects who discontinued due to reasons other than lack of efficacy or adverse events will be imputed under the MAR assumption.

These two steps will be carried out sequentially to construct 100 hypothetical complete data sets.

An ANCOVA model (not repeated measures, and with no random effects) with the following covariates will be performed for each imputation using the SAS Mixed procedure:

- HGB = Baseline Hemoglobin category (≥ 11 or < 11 g/dL)
- CKD = CKD Stage (3, or 4/5)
- TRT = Treatment group
- BASE = Baseline hemoglobin value

The SAS MIAnalyze procedure will be used to combine the results of these analyses for the imputations. The overall least square means, standard errors, 95% confidence intervals, and p-values will be reported.

Reasons for subject discontinuation that are identified as lack of efficacy will be discussed and finalized prior to database lock.

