5.6.1. MMRM

All PRO assessments will be included for this analysis. The analysis will be based on observed data, i.e., data collected at each timepoint without carrying forward previous values. Data from a limited number of PRO assessments may be used in case of substantial dropout (i.e., analysis will be limited to timepoints at which at least 10% of patients have non-missing data in both treatment groups).

The response variable will be the change from baseline to each PRO assessment. The model will include the treatment arm (ziltivekimab vs. placebo) and timepoint (Week 5, Week 13, and week 24) as fixed-effect categorical factors, the baseline PRO score and stratification factors (baseline haemoglobin (≥ 11 or < 11 g/dL) and CKD stage (3, 4 or 5)), as well as the baseline PRO score x time and treatment x time interactions. Both main effects and the interaction terms will remain in the model, regardless of significance. The model will present least squares (LS) mean estimates for each dose, least squares mean differences of each study drug dose from placebo, standard errors, 95% CIs and p-values (where applicable) for mean changes from baseline to each visit. A plot of the LS means accompanied by the 95% CI will be produced.

In addition, an overall adjusted mean estimate will be derived that will estimate the average change from baseline across all time points, giving each visit equal weight.

The standardized mean difference (SMD) including 95% CI (Hedges' g) will also be provided.

The MMRM analysis will be conducted using PROC MIXED in SAS. The model will assume unstructured covariance among the within-patient repeated measurements. If the algorithm does not converge, a heterogeneous Toeplitz (the TOEPH option in SAS PROC MIXED) will be tried first and then AR(1) as a covariance structure to achieve convergence. The Kenward-Roger approximation will be used to estimate denominator degrees of freedom.

Variables listed as categorical in the list above will be included in the CLASS statement of the procedure. The unique patient identifier will also be included as a class variable. A REPEATED statement over the visits will be included with the unique patient identifier as the SUBJECT variable in the REPEATED statement.

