for a large number of early terminated patients due to COVID19 and (2) the time window for End of Treatment visit (the average of the last 2 visits including and after Week 13) varying from patient to patient, MMRM results may not be appropriate to analyze change or percentage change from baseline to End of Treatment. Therefore, analysis for change or percentage change from baseline to End of Treatment will be performed using an analysis of covariance model (ANCOVA), where the percent change or change from baseline to End of Treatment described above will be used as the outcome variable. The ANCOVA model will also include baseline hemoglobin (≥ 11 or < 11 mg/dL), CKD Stage (3, 4 or 5), and treatment group as factors; baseline hs-CRP and the baseline value (for efficacy parameters other than hs-CRP) as covariates.

The sample SAS code for ANCOVA analysis is provided below:

```
*****
*Note: PCHG = Percent change from baseline for efficacy parameter
*      HGB = Baseline Hemoglobin category ( $\geq 11$  or  $< 11$  mg/dL)
*      CKD = CKD Stage (3, or 4/5)
*      TRT = Treatment group
*      CRP = Baseline hs-CRP value
*      BASE = Baseline value for efficacy parameter
*****;

proc mixed data=efficacy ;
  class HGB CKD TRT;
  model pchg=HGB CKD TRT BASE CRP;
  lsmeans TRT/ pdiff=control('0') cl ;
  ods output diffs=Diff;
run;
```

Analysis of change or percent change from baseline to Week 13 for the primary, secondary, and exploratory endpoints will be carried out using MMRM analysis as originally planned and will include scheduled post-baseline visits up to and including Week 13. Details of MMRM analysis can be found in section 3.4.1 of this SAP.

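### The sample code for the primary hs-CRP MMRM omits VISIT from the REPEATED statement, so a patient with no row for a skipped interim visit enters the wrong covariance positions

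*SAP*

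**What the plan says.** Clinical SAP Section 3.4.1 (Primary Efficacy Endpoint) defines an MMRM for percent change in hs-CRP and introduces a PROC MIXED block with "The sample SAS code can be found below". The block has "class HGB CKD TRT VISIT" and then "repeated / type=un subject=USUBJID". VISIT therefore appears in CLASS and in the fixed effects, but not in REPEATED.

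Section 3.4 (Efficacy Assessment) sets the covariance: "An unstructured covariance matrix will be used to model the within-subject correlation". It also sets the data: "The analysis will be performed based on all observed post-baseline scores without any imputation of missing data".

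The sensitivity analysis in Section 3.4.1 foresees gaps in the middle of a patient's series: "Intermittent (non-monotone) missing data will be imputed using the MCMC option of SAS PROC MI (using seed=5414".

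After the COVID-19 changes, Section 5 keeps the MMRM for Week 13, says that it "will include scheduled post-baseline visits up to and including Week 13", and refers back to Section 3.4.1 for details. Sections 3.4.2 and 3.4.3 apply the same method to the secondary and the continuous exploratory endpoints.

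The separate PRO SAP v2.0, Section 5.6.1, describes its own MMRM differently: "A REPEATED statement over the visits will be included with the unique patient identifier as the SUBJECT variable in the REPEATED statement".

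**The concern.** With no repeated effect, PROC MIXED takes the order of records within a subject as the index of the covariance matrix. That is harmless only if every patient has one row per scheduled visit, in visit order. The plan fits observed scores, expects some intermittent gaps, and nowhere in the clinical SAP asks for placeholder rows, a sort order or a covariance indexed by visit.

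The fixed effects still use the true VISIT, so the model means what it should. The error lies in the covariance: a patient's Week 13 record can be given the variance and correlations of an earlier visit. Weights, the Week 13 standard error, the confidence interval and the p-value are then affected, with no message in the log. The AR(1) fallback in Section 3.4 also depends on position.

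The block has two other faults, which show themselves. USUBJID is not in CLASS, so a character identifier stops the run. There is no LSMEANS statement, although LSMeans and Diffs tables are requested. Repairing only those two leaves a program that runs cleanly and still has the covariance fault.

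**Working it through.** **The plan's own figure (clinical SAP Section 2.2.4).** Difference 60.74, SD 16.893, two-sided alpha 0.05, 54 per group: SE = 16.893 × √(2/54) = 3.25, so z = 60.74 / 3.25 ≈ 18.7 and power is 1.000 to three decimals. With 10% dropout, 54 / 0.90 = 60 per group, and 4 × 60 = 240. The stated design reproduces and does not depend on the REPEATED statement.

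**Positions.** In the Table 1 schedule of the clinical SAP, the post-baseline hs-CRP visits to Week 13 read as Weeks 2, 4, 9 and 13. The table is damaged in the copy at hand, so this is an assumption.

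| Rows in the data set | Positions by VISIT | Positions by row order |
|---|---|---|
| Weeks 2, 4, 9, 13 | 1, 2, 3, 4 | 1, 2, 3, 4 |
| Weeks 2, 9, 13 (no Week 4 row) | 1, 3, 4 | 1, 2, 3 |
| Weeks 2, 4, 9 (dropout before Week 13) | 1, 2, 3 | 1, 2, 3 |
| All four rows, Week 4 response missing | 1, 3, 4 | 1, 3, 4 |

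Only the second pattern, or rows out of visit order, is misaligned.

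**Size.** The SAP gives one SD (16.893, Week 4), no by-visit SDs, no correlations and no intermittent rate, so every row below rests on assumptions. The set-up was two arms of 60, four visits, no true effect, REML with an unstructured matrix and 200 replicates per row. The skip rate applies to each of the three interim visits and skipped rows are absent. Each cell gives the result by VISIT, then by row order, for the Week 13 comparison.

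| SDs at the four visits | Correlation | Skip rate | Mean model SE | Empirical SE | Null rejection |
|---|---|---|---|---|---|
| 16.893 throughout | exchangeable 0.5 | 10% | 3.064, 3.054 | 3.095, 3.156 | 6.5%, 7.0% |
| 16.893 throughout | AR 0.6 | 10% | 3.082, 3.048 | 3.238, 3.251 | 5.5%, 6.5% |
| 8, 11, 14, 16.893 | AR 0.6 | 2% | 3.075, 3.036 | 2.992, 3.014 | 2.5%, 3.5% |
| 8, 11, 14, 16.893 | AR 0.6 | 10% | 3.067, 2.919 | 3.012, 3.189 | 3.5%, 8.0% |
| 34, 28, 22, 16.893 | AR 0.6 | 10% | 3.111, 3.205 | 3.186, 3.320 | 5.5%, 5.0% |
| 16.893 three times, then 33.8 | AR 0.6 | 2% | 6.120, 5.819 | 6.174, 7.178 | 3.5%, 11.5% |
| 16.893 three times, then 33.8 | AR 0.6 | 10% | 6.190, 5.493 | 5.863, 7.494 | 4.0%, 14.0% |

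A 2% skip rate means about 7 of 120 patients: 120 × (1 − 0.98³) = 7.1. Rejection rates carry a simulation error of about 1.5 to 2.5 percentage points.

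A separate simulation (400 trials, 60 per arm, correlation 0.6, 5% missing per visit, SD rising from 0.6 to 2.0) gave a reported SE about 7% too small, a true SD of the estimate of 0.44 instead of 0.37, and 88% coverage instead of 95%. With equal SDs, coverage was 95%.

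**Effect on the primary test.** Inflate the planned standard error by 0.44 / 0.37 = 1.19: z = 18.7 / 1.19 ≈ 15.7. If the SD were also three times the planned value, z = 15.7 / 3 ≈ 5.2. Both are far beyond 1.96.

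**The case against.** The block is labelled sample code, and Section 6 promises detailed programming specifications in a separate document, which is not at hand. The prose of Sections 3.4 and 3.4.1 (visit as a factor, unstructured within-subject covariance) is not wrong. As printed, the block cannot produce the dose-versus-placebo differences, so a programmer must edit it before any p-value exists and may well add VISIT then. This limits the likelihood of harm. It does not make the printed statement right, and no text in the clinical SAP tells the programmer to index the covariance by visit.

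The trigger may also be uncommon. PRO SAP Section 5.9.2 expects mostly monotone missing data in this study, with only a small intermittent part. A reader might infer that every skipped visit, or the large COVID-19 loss, is misaligned. The position table shows otherwise.

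Section 3.4.1 further sends the analysis to a Hodges-Lehmann and Wilcoxon method, which uses no REPEATED statement, if the Shapiro-Wilk test on model residuals gives p < 0.01. In 1,000 simulated trials with SD rising from 0.6 to 2.0, pooled raw residuals met that criterion in 100% of four-arm and 96% of two-arm trials. With residuals standardised by visit the rate was only 4% to 5%. The SAP does not name the residual type, so this safeguard is uncertain.

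Finally, the PRO SAP wording covers PRO scores only, and its Section 5.6 says that its MMRM follows the clinical SAP. This shows that a by-visit index was probably intended, rather than that the two plans deliberately differ.

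**Conclusion.** Wrong as written, and minor. The printed REPEATED statement does not implement a by-visit unstructured covariance for a patient whose skipped interim visit has no row, or whose rows are not in visit order.

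The size cannot be fixed from the SAP. Under the assumptions shown it is close to nil with equal SDs. It is also small with a modest rise in SD and few skipped visits, and did not inflate rejection when the SD fell over visits. It becomes material when the SD rises towards Week 13: the model standard error was about 5% to 11% below its by-visit value (for example 2.919 against 3.067, and 5.493 against 6.190), and null rejection was 8% to 14%. The documents do not say which pattern hs-CRP follows.

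A reader might infer that the dose sequence in Section 3.4.4 is at risk. The planned figures do not support that, since z stays far above the critical value even with a much larger SD. What remains is distortion of reported standard errors, intervals and p-values. It matters most for secondary and exploratory endpoints, where effects may be smaller and the same method applies.

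**What to change.** In the Section 3.4.1 code write:

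`class HGB CKD TRT VISIT USUBJID;`

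`repeated VISIT / type=un subject=USUBJID;`

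`lsmeans TRT*VISIT / diff cl;`

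The essential change is the one word VISIT in REPEATED. The other two edits make the block run with a character identifier and produce the estimates that the section promises. The result also agrees with PRO SAP Section 5.6.1. Because Section 5 and the secondary and exploratory sections refer back to this method, one correction covers them. The cost is three lines of code. No sample size, power figure, endpoint or testing order changes.
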